9.0 Study Withdrawal/Discontinuation

Study participants may contact the study team if they wish to withdraw.

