Adolescents' glycemic control will be assessed with HbA1c, which is obtained as part of regular clinical care. For adolescents who do not have an HbA1c value associated with a clinic visit (due to social distancing requirements), we will request that they use a mail-in kit. The kit includes clear instructions to provide a dried blood spot that is mailed to the lab (Coremedica). When the lab value is available, KSP will notify study participants.

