If adolescents endorse items on the Youth Self Report (YSR) measure pertaining to suicide or self-harm, we will follow the following procedure for self-harm assessment. Item 18 asks individuals to rate from 0-2 (how often) "I deliberately try to hurt or kill myself." Similarly, item 91 reads "I think about killing myself." Scores of 1 indicate "sometime" and 2 indicate "usually." When the YSR is given during study enrollment, researchers will immediately check items 18 and 91. If a 1 or 2 is indicated on either of these items, the Pediatric Endocrinology social worker will be paged and will complete a risk assessment following clinic protocol. The PI will also be notified. If the clinic social worker is not available, research staff will administer the Columbia Suicide Severity Rating Scale (C-SSRS). If information gathered from the C-SSRS indicates low risk (non-specific ideation, no plan), individuals will be given information on local behavioral health resources and informed that the PI will check in with them within the next 48 hours. If the C-SSRS indicates high risk or risk is ambiguous the clinic social worker will be contacted again for further assessment and/or to transfer the patient for psychiatric evaluation. If the clinic social worker cannot be reached, the researcher will accompany the patient and their caregiver to the Children's Emergency Department for psychiatric evaluation.

We will download data from the Facebook group including posts, comments, and reactions from the participants so that we can study this data to better understand how people participate and how much response our posts garnered from the group. We will not download any data from participants' Facebook profiles or any posts to their feeds - only the posts, comments, and the posts/comments participants react to in the study Facebook group.

All children will receive clinical care throughout the course of the study. All diabetes treatment decisions will be made by the diabetes treatment team. All patients have access to the treatment team 24 hours/day and 7 days per week. Participants will be informed that they may discontinue the study at any time or skip any questions they do not feel comfortable answering. There are no potential legal or social risks to participants consenting to participate in this investigation. Parents will be told to follow the diabetes clinic providers' guidance on any questions related to diabetes management.

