Exploratory Aim: Examine the differential impact of intervention effects across demographic factors (i.e., marital status, income, adolescent age, and sex).

While evaluating the main effects of interventions is critical to improving health outcomes, it is equally important to examine moderators of randomized clinical trials – even those that are unsuccessful – in order to determine *for whom* interventions may work. Based on findings from the literature and our own earlier work, we will examine potential moderators, with a focus on marital status, income, and adolescent age and sex. Moderators will be tested by including an interaction term with treatment group in the regression models.

Power and sample size:

We plan to enroll 154 subjects so that, after allowing for a 15% attrition rate, 130 subjects will be available for analysis. Preliminary data from our pilot study with 30 adolescents indicates that mean A1C is 9.0% with a standard deviation of 1.16% and a correlation between repeated measurements over time of 0.60. Under these assumptions, we will have 80% power to detect a 0.5% difference in A1C if 122 subjects are measured at all 4 time points or if 138 subjects are measured only twice (out of 4 possible time points). Since we expect to obtain ≥ 3 measurements on most of subjects, enrolling 130 subjects with 2 to 4 measurements each will provide sufficient power for Aim 1. For the SCI (a measure of adherence), using preliminary data in 30 subjects we estimated baseline scores of 23.6 ± 4.2 with a correlation among repeated measures over time of 0.82. With 130 subjects measured at least twice, we will have 80% power to detect a 2.0 unit change due to treatment, which is an 8.5% difference from baseline.

Power calculations for mediation models were considered assuming 130 subjects will be available for analysis. In preliminary data, partial correlations of the mediators, PHQ9 and DFC, with A1C were 0.20 and 0.51, respectively. Correlations of the mediators with treatment were 0.52 and 0.54, respectively. Under these assumptions, we have 63% power to detect an indirect effect of treatment on A1C through PHQ9 and >99% power to detect an indirect effect of treatment on A1C through DFC. Calculations assume a 0.05 significance level.

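### The follow-up A1C kit is tied to social distancing, and the protocol does not say whether outcomes are still collected after a mother stops, so recoverable A1C values may be lost

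*Combined protocol and SAP*

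**What the plan says.** **Leaving.** Section 9.0 (Study Withdrawal/Discontinuation) is one sentence: "Study participants may contact the study team if they wish to withdraw". Section 7.0 (Risks) adds: "Participants will be informed that they may discontinue the study at any time or skip any questions they do not feel comfortable answering". Neither distinguishes stopping the intervention, stopping surveys and withdrawing all consent, and neither distinguishes the mother from the adolescent.

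**A1C.** Section 5.0 (Enrollment/Randomization) states: "Adolescents' glycemic control will be assessed with HbA1c, which is obtained as part of regular clinical care". The fallback is introduced with the words "For adolescents who do not have an HbA1c value associated with a clinic visit (due to social distancing requirements"), and then "we will request that they use a mail-in kit". The same section has a kit mailed to every participating mother within days of enrollment.

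**Surveys.** Under section 6.0, mothers and adolescents each complete their own measures at baseline, 3, 6 and 12 months. Follow-up is linked to regular clinic visits.

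**Analysis.** Section 10.0 (Effects of the Intervention) analyses a subject who has the outcome at baseline and at 6 or 12 months or both. Under its heading on dropout bias, section 10.0 describes dropouts as subjects who do not come back for follow-up. It says they are frequently not a random sample and plans a logistic regression of dropout status on baseline variables. For sample size, 154 are enrolled so that "after allowing for a 15% attrition rate, 130 subjects will be available for analysis".

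**The concern.** The mother receives the intervention (7 calls and 3 months of daily posts), but Aims 1 and 2 are about the adolescent's outcomes. Much of that information does not depend on the mother's participation: A1C is a clinic measurement, and adolescents answer their own surveys. The visible text has no rule that keeps it coming once the mother stops.

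The kit wording is the more specific problem, because it is a stated condition and not a silence. Families who skip visits, move away or disengage are the ones most likely to have no clinic A1C, and their reason is not social distancing. If their diabetes care is also slipping, the missing values are informative. The planned logistic regression would show who was lost but would not bring back a value that was never taken.

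**Working it through.** **1. Trace one missing clinic A1C through the text.**

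- Enrollment: a kit is mailed to every participating mother, with no reason required. This does not provide for 3, 6 or 12 months.
- Follow-up, clinic value missing because of distancing: the family is asked to use a kit.
- Follow-up, clinic value missing for another reason: no source is named, so on a literal reading there is no A1C at that visit.
- If both the 6- and 12-month values are missing, section 10.0 excludes the adolescent from the A1C analysis, even with baseline and 3-month values. One kit result at 6 or 12 months would bring the adolescent back in.
- The dropout analysis in section 10.0 predicts dropout status. It does not adjust the treatment effect.

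**2. Reproduce the plan's own figures (section 10.0, Power and sample size).** Inputs: SD 1.16, correlation 0.60, difference 0.5, power 80%, equal allocation, alpha 0.05 (taken as two-sided, which reproduces the stated sizes), 15% attrition.

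- Enrollment: 130 / (1 − 0.15) = 152.9, so 153 against 154 stated. Forward, 154 × 0.85 = 130.9.
- SD of the mean of m equally correlated measurements: 1.16 × √[(1 + (m − 1) × 0.60) / m]. This is 1.16 × √0.80 = 1.038 for m = 2 and 1.16 × √0.70 = 0.971 for m = 4.
- Total N for a two-sample comparison: 136 (normal) or 138 (t) for m = 2, against 138 stated; 120 (normal) or 122 (t) for m = 4, against 122 stated.

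The stated figures reproduce.

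**3. What recovery could be worth.** Planned losses are 154 × 0.15 = 23.1 dyads. The documents do not say what share f of these could still give an A1C, so f is varied as an assumption. N = 130.9 + 23.1f. The ratio of the standard error to that at 130.9 is √(130.9 / N). Power is for a 0.5-point difference, from the noncentral t, and assumes recovered dyads contribute as many measurements as the others.

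| f | N | SE ratio | Power, 2 measurements | Power, 4 measurements |
|---|---|---|---|---|
| 0 | 130.9 | 1.00 | 78.1% | 83.3% |
| 0.5 | 142.5 | 0.96 | 81.5% | 86.3% |
| 1 (upper bound) | 154.0 | 0.92 | 84.4% | 88.8% |

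The gain at the upper bound is 84.4 − 78.1 = 6.3 power points with two measurements and 88.8 − 83.3 = 5.5 with four.

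**4. Bias.** I give no figure. It would need dropout rates by arm and the gap in A1C between those lost and those kept, and the documents give neither. The model also includes baseline, so a gap already present at baseline would largely cancel. What matters is a difference in change since baseline.

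**The case against.** A reader might infer that the protocol makes leaving all-or-nothing, so that a mother who stops calls or Facebook takes her adolescent's outcomes with her and the effect is estimated only among engaged dyads. The documents do not support this. Section 6.0 ties follow-up to clinic visits, not to calls. Section 10.0 sets an 80% call-attendance benchmark, so missed calls are expected within the study. It describes dropout as not returning for follow-up, and it selects subjects by measured outcomes with no attendance condition. A dyad with no calls but with baseline and 6-month A1C is analysed. Sections 7.0 and 9.0 are silent on this; they do not order data collection to stop. Consent pages are not in the text available for review, and permission to continue may sit there.

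Timing also limits the argument. Calls and posts end at about 3 months, so a loss after that point cannot be a mother stopping them. The share of the 15% attrition due to stopping the intervention is unknown, and some families will withdraw all consent.

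On the kit, the bracketed words may only explain why kits were introduced, and no text says that a family missing a visit for another reason is refused one.

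Most of this stands, and it keeps the point small. It does not settle follow-up A1C. The kit offer is worded with a condition, the enrollment kit does not cover later visits, and the analysis rule makes the 6- and 12-month values decisive. This part of the point applies whether or not the mother stopped the intervention.

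**Conclusion.** This is a cheap improvement, not an error in the design or the sample size. Two things hold. The visible protocol does not say whether A1C and adolescent surveys continue after a mother stops the intervention or the surveys. And, read literally, it leaves an adolescent who misses a clinic A1C for a reason other than distancing without a follow-up value, which can remove that adolescent from the A1C analysis.

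At most about 23 of 154 dyads are affected if losses run as planned. If half were recovered, the standard error would fall by about 4%; if all, by about 8%. The second is a ceiling, because it supposes that every planned loss consents and gives a value. The better reason to act is that the plan itself regards dropouts as often non-random and relies on describing them. The size of any bias cannot be stated from the documents.

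**What to change.** 1. In section 5.0, delete the bracketed social-distancing condition, so that the existing kit goes to any consenting adolescent without a clinic A1C at 3, 6 or 12 months.
2. In section 9.0, state that stopping calls or Facebook does not end outcome collection for mother or adolescent. State that a dyad stopping surveys is asked for permission to keep taking clinic A1C from the record, and treat full withdrawal of consent as a separate choice.
3. Record the date, level and reason of stopping, by arm.

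The cost is a short protocol and consent amendment, a few more kits of a type already in use, and a place to record stopping in REDCap. The downside is slightly more kit-based A1C values among the clinic ones. If the consent form already gives these permissions, the change to 9.0 reduces to saying so.

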10.0 Statistical Considerations

Baseline variables known to be associated with parenting including age, sex, income, and marital status will be compared by treatment group using the Kruskal-Wallis test (continuous variables) or Pearson's Chi-squared test (categorical variables). We will also examine if diabetes-related variables (e.g., duration of diabetes, baseline A1C) are associated with treatment group. *A priori*, we assume that our block randomization will lead to well-balanced groups so that we will not need to control for additional confounders.

Effects of the Intervention: We will estimate the effect of the intervention on each of the continuous outcomes by fitting linear mixed-effects models developed. In modeling, outcomes will be considered at their key time-points (baseline, 3 months, 6 months, and 12 months) with treatment group and the interaction of treatment with time serving as the main explanatory variables. Such a model will allow us to test for any differences between treatment and control groups over time while accounting for baseline values. While the randomized block design should minimize confounding, we will adjust for age, income, and marital status to improve precision. The results from the adjusted and unadjusted models will be compared with respect to their estimates of the treatment effects. Our interpretation will focus on describing clinically relevant treatment effects (e.g., A1C reductions of $\geq 0.5\%$, >1 additional glucose check per day, reduction from moderate to mild depressive symptoms) with corresponding confidence intervals, rather than just significance testing. We will include a random intercept to account for within-subject correlation. The error structure of the model is assumed to be compound symmetric, and the validity of this assumption will be examined by computing Akaike Information Criteria against other common structures. Subjects will be included in the analysis if they have an outcome measured at baseline and at least one outcome measured 6 or 12 months later.

Examining mediators will provide evidence for the mechanisms of change, offering direction for program implementation and future research. Investigating mediators of the intervention also allows us to test the theoretical basis and the effect of intervention on separate outcomes,¹⁰⁷ such as glycemic control, and psychosocial outcomes. To assess direct and indirect effects of potential mediator variables, we will follow the steps outlined by MacKinnon and colleagues^{108,109} to establish mediation. The bootstrap method will be used to obtain a 95% confidence interval for the total, direct, and indirect effects. We will test maternal depressive symptoms and parental involvement as mediators of treatment effects, maintaining consistent temporal ordering, by considering baseline randomized treatment, 3-month depressive symptoms and parental involvement variables as the mediators, and 6-month outcomes (treatment effects), as well as 12-month outcomes (sustained treatment effects). Our longitudinal data will also allow us to consider additional analyses that account for the bidirectional relationships between family functioning and depressive symptoms.

To determine the feasibility of the intervention, we will examine recruitment and retention data. In addition, fidelity checks will be conducted by reviewing 20% of the telephone sessions, which will be coded for content by an independent rater. We propose a feasibility benchmark of $\geq 90\%$ fidelity. To evaluate acceptability of the intervention, we will examine participation (phone call attendance), adherence (completion of homework), and satisfaction ratings. We propose a feasibility benchmark of $\geq 80\%$ attendance. We will also conduct exit interviews with mothers, which will be analyzed with a content analysis approach to identify themes across participants.

[figure not shown]
Assessing biases caused by dropouts: Some subjects may not return for their follow-up visit and hence have missing values of their response variables. Frequently, such subjects ("dropouts") are not a random sample of the entire cohort and an analysis of only the complete cases will bias the results. Indirect information about the nonrandom dropouts will be obtained by using binary logistic regression to predict dropout status on the basis of all baseline predictor variables.

Exploratory Aim: Examine the differential impact of intervention effects across demographic factors (i.e., marital status, income, adolescent age, and sex).

While evaluating the main effects of interventions is critical to improving health outcomes, it is equally important to examine moderators of randomized clinical trials – even those that are unsuccessful – in order to determine *for whom* interventions may work. Based on findings from the literature and our own earlier work, we will examine potential moderators, with a focus on marital status, income, and adolescent age and sex. Moderators will be tested by including an interaction term with treatment group in the regression models.

Power and sample size:

We plan to enroll 154 subjects so that, after allowing for a 15% attrition rate, 130 subjects will be available for analysis. Preliminary data from our pilot study with 30 adolescents indicates that mean A1C is 9.0% with a standard deviation of 1.16% and a correlation between repeated measurements over time of 0.60. Under these assumptions, we will have 80% power to detect a 0.5% difference in A1C if 122 subjects are measured at all 4 time points or if 138 subjects are measured only twice (out of 4 possible time points). Since we expect to obtain ≥ 3 measurements on most of subjects, enrolling 130 subjects with 2 to 4 measurements each will provide sufficient power for Aim 1. For the SCI (a measure of adherence), using preliminary data in 30 subjects we estimated baseline scores of 23.6 ± 4.2 with a correlation among repeated measures over time of 0.82. With 130 subjects measured at least twice, we will have 80% power to detect a 2.0 unit change due to treatment, which is an 8.5% difference from baseline.

Power calculations for mediation models were considered assuming 130 subjects will be available for analysis. In preliminary data, partial correlations of the mediators, PHQ9 and DFC, with A1C were 0.20 and 0.51, respectively. Correlations of the mediators with treatment were 0.52 and 0.54, respectively. Under these assumptions, we have 63% power to detect an indirect effect of treatment on A1C through PHQ9 and >99% power to detect an indirect effect of treatment on A1C through DFC. Calculations assume a 0.05 significance level.

Power for moderation will depend on the effect size of the moderation and if the moderator is measured on a continuous or categorical scale. For continuous moderators (adolescent age), we have 80% power to detect a 0.36% change in the treatment effect on A1C per 1-sd change in the moderator. For a binary moderator (frequency 50%), we have 80% power to detect a modification of the treatment effect on A1C of 0.55%. All calculations assume $\alpha=0.05$.

Despite evidence demonstrating the effectiveness of telephone-based CBT to reduce depressive symptoms, there is a chance that mothers who receive the intervention will not report reduced depressive symptoms. If this happens, we would examine the data to determine for whom the intervention works. For example, it may be that a more limited range of scores on the screening tool (PHQ-9) predicts a better response to the intervention.

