5.0 Enrollment/Randomization

Participants will be enrolled from the Children's Diabetes Program at Vanderbilt.

Due to the COVID-19 pandemic and social distancing requirements, a remote recruitment and enrollment protocol was established. KSP will review the diabetes clinic schedule, and participants who meet initial eligibility criteria (age, date of diagnosis) will be called the week of their clinic visit. The RA will introduce the study, and if mothers are interested, verbal consent for the screening questionnaire will be obtained. Mothers who consent will be emailed a link to the screening survey in REDCap. The RA will then email the mother to let her know if she is eligible or not. Eligible mothers will be asked to schedule a time for enrollment. At the preferred time, the mother and adolescent will be called, and the RA will provide each with a full description of the risks and benefits of the study. If they agree to participate, they will be emailed the link to sign the eConsent form in REDCap. The RA will stay on the phone while these are signed to answer any questions. Once consent/assent forms are signed, the parent and adolescent will be emailed links to complete the study surveys in REDCap. The mother will be asked to text the RA when these are completed or if they have any questions. The final enrollment will take place over the phone (demo text message and Facebook friending).

After completing all baseline data, mothers will be given instructions to "friend" the study Facebook account. Once the mother has established a connection to the study Facebook account, the mother-adolescent dyad will be randomly assigned to the intervention condition or attention control (equal numbers in each group).

Randomization will be stratified by the adolescents' treatment type (insulin pump vs. injections) and use of continuous glucose monitoring (CGM or no CGM) to remove the possibility of confounding by differences related to insulin regimen. Randomization will be determined by a computerized program created by the biostatistician on the project ([name]).

Participating mothers will be mailed a study binder and an A1C mail-in kit within 2-3 days of enrollment.

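### The mixed model estimates a baseline arm difference that randomisation already sets to zero, which adds about 20% to 30% avoidable variance to the A1C contrasts, and it omits the stratification factors

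*Combined protocol and SAP*

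**What the plan says.** Section 10.0 (Effects of the Intervention) specifies linear mixed models with a random intercept and compound symmetry. Outcomes enter at "their key time-points (baseline, 3 months, 6 months, and 12 months) with treatment group and the interaction of treatment with time" as the main explanatory variables. The model is said to "test for any differences between treatment and control groups over time while accounting for baseline values", but no mechanism is given beyond the model itself: arms are not constrained to a common baseline mean, and the baseline outcome is not named as a covariate.

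The adjusted version is described thus: "we will adjust for age, income, and marital status to improve precision". The analysis set is restricted to subjects with "an outcome measured at baseline and at least one outcome measured 6 or 12 months later".

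Section 5.0 stratifies randomisation by "treatment type (insulin pump vs. injections) and use of continuous glucose monitoring (CGM or no CGM". Neither factor appears in any model in Section 10.0.

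No single A1C contrast is named as primary. The power paragraph claims "80% power to detect a 0.5% difference in A1C if 122 subjects are measured at all 4 time points", which is a time-averaged calculation. The effects paragraph tests differences over time. The mediation paragraph separates "6-month outcomes (treatment effects), as well as 12-month outcomes (sustained treatment effects".

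**The concern.** With a treatment main effect and treatment-by-time terms both free, the model estimates an arm difference at baseline, and each treatment-by-time term is a difference in change. Among all randomised dyads the true baseline difference is zero, so estimating it spends information on a known quantity.

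The covariates meant to improve precision do almost nothing for this contrast. Age, income and marital status are treated as fixed over time, so as main effects they cancel from a change contrast when data are complete. The same holds for the pump and CGM factors: they would sharpen the contrast only once baseline is constrained or used as a covariate.

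What is at stake is the width of the intervals. Section 10.0 rests interpretation on confidence intervals around effects such as a 0.5% A1C reduction, and the amendment log records enrolment below expectation, so precision that needs no extra data is worth having.

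**Working it through.** **Inputs (Section 10.0, power paragraph):** A1C SD 1.16, correlation ρ = 0.60, difference 0.5%, α = 0.05 (taken as two-sided), 130 analysed, 1:1 allocation (Section 5.0). Compound symmetry comes from the effects paragraph.

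**Reproducing the plan's figures.** The variance factor for a mean of k measurements is (1 + (k−1)ρ)/k, which is 0.70 for k = 4 and 0.80 for k = 2. A noncentral-t calculation then gives 122 and 138 in total, exactly as stated, so the inputs are usable. At 130 subjects with four visits, this time-averaged contrast has 83.0% power.

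**Planned and constrained variance (units of σ²).**
- One follow-up visit: planned 2(1−ρ) = 0.80; constrained 1−ρ² = 0.64. The saving is (1−ρ)/2 = 20%.
- Mean of three follow-ups, with m = (1+2ρ)/3 = 0.7333: planned m + 1 − 2ρ = 0.5333; constrained m − ρ² = 0.3733. The saving is 0.16/0.5333 = 30%.

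Exact generalised least squares for the four-visit model gives the same ratios.

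**At N = 130, complete data.** SE = √(4 × factor × 1.16² / 130); half-widths use t with 128 df.

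| Contrast | SE | 95% half-width | Power for 0.5% |
|---|---|---|---|
| One visit, planned | 0.182 | 0.36 | 77.8% |
| One visit, constrained | 0.163 | 0.32 | 86.2% |
| Mean of three, planned | 0.149 | 0.29 | 91.6% |
| Mean of three, constrained | 0.124 | 0.25 | 97.9% |

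For the joint 3-df treatment-by-time test with a constant 0.5% effect, the noncentrality rises from 11.32 to 16.17 and power from 81.6% to 93.7%.

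**Sensitivity to ρ** (the 0.60 comes from a 30-adolescent pilot).

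| ρ | One-visit saving | Mean-of-three saving |
|---|---|---|
| 0.4 | 30% | 45% |
| 0.5 | 25% | 37.5% |
| 0.6 | 20% | 30% |
| 0.7 | 15% | 22.5% |
| 0.9 | 5% | 7.5% |

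If time were linear rather than categorical, the saving on the slope difference at ρ = 0.60 would be 16.7%.

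**Incomplete data (assumed patterns).** Per arm, of 65: 35 complete; 8 at 0, 6 and 12 months; 6 at 0, 3 and 12; 6 at 0, 3 and 6; 5 at 0 and 12; 5 at 0 and 6.
- 12-month SE 0.194 to 0.176, a 17.6% saving.
- Mean-of-three SE 0.155 to 0.132, a 27.5% saving.
- With 24 more dyads that lack a 6- or 12-month value (per arm, 6 with baseline and 3 months, 6 with baseline only), the savings are 15.4% and 25.4%.

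**Covariates (assumed R² of 5%, 10% and 20%).** In the planned contrast with complete data the SE stays at 0.182 throughout; in both incomplete patterns the variance gain is under 1%. Once baseline is constrained, the total one-visit saving becomes 21.1%, 22.2% and 25.0%.

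**SCI (ρ = 0.82).** The one-visit saving is (1−0.82)/2 = 9%, with no material effect on power.

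**The case against.** The strongest reply is that the plan is valid, conventional and adequately powered. Its own time-averaged contrast exceeds 80%, as do the planned mean-of-three and joint tests. Only the single-visit change contrast falls short, at 77.8%, and no section names that as the A1C test. This stands, and it limits the point to efficiency.

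A second reply is that the text writes no equation, so a constrained model may be intended. But treatment group is listed as a term alongside its interaction with time, so a free baseline difference is the natural reading. If a constrained model is meant, one sentence would say so.

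A third is that baseline equality holds for all randomised dyads, not for the retained subset. This also stands, and it cuts both ways. Let D be the baseline imbalance in the retained subset:
- If dropout depends on measured baseline, the change contrast shifts by −(1−ρ)D and the baseline-adjusted one by 0. A simulated null with about 15.5% loss per arm and D = −0.160 gave +0.063 and −0.001.
- If dropout depends on the unmeasured stable level, the shifts are 0 and (1−ρ)D. With D = −0.126 the simulation gave −0.001 and −0.053.

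Either way the shift is 0.04 per 0.10 A1C points of imbalance. This supports lifting the inclusion rule and keeping the free-baseline model as a sensitivity analysis; it does not favour one model throughout.

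Finally, the gain from the strata cannot be sized, because the documents give no association of pump or CGM use with A1C. That part stands as a mismatch between design and analysis.

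**Conclusion.** The point holds. Read as written, the model leaves about 20% (one visit) to 30% (mean of three visits) of the A1C contrast variance avoidable, given ρ = 0.60, compound symmetry, categorical time and complete data. Under the assumed incomplete patterns this is about 15% to 18% and 25% to 28%. The exact size depends on a correlation from a small pilot and on a contrast the plan does not name, but the saving is positive for any ρ below 1. It is a loss of precision, not a bias and not a failure of the stated power. A 20% saving is equivalent to analysing about 162 dyads instead of 130 (130/0.80). The change should be made because it needs no new data.

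**What to change.** Name one primary model and one primary contrast for A1C.

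- **Model.** Use a baseline-constrained mixed model: visit effects plus treatment-by-visit terms at 3, 6 and 12 months, with no treatment term at baseline. An alternative is a post-baseline model with baseline outcome-by-visit as a covariate.
- **Analysis set.** Include every randomised dyad with a baseline or any follow-up value, in place of the 6- or 12-month rule.
- **Covariates.** Add the pump/injection and CGM factors to age, income and marital status.
- **Sensitivity analyses.** Keep the unadjusted model and the free-baseline model.
- **Timing of baseline A1C.** Section 5.0 randomises after baseline data are complete, yet also says "Participating mothers will be mailed a study binder and an A1C mail-in kit within 2-3 days of enrollment". If any baseline A1C was collected after randomisation through that kit, repeat the analysis without those values; the constrained model still keeps such dyads.

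The cost is analysis-plan wording, using variables already collected. The strata use 2 to 3 degrees of freedom. The baseline-covariate version loses any dyad without a baseline value; the constrained version does not.
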